2.1 Assessment and management of risk

Aspirin and ticagrelor are both widely used as antiplatelet drugs for the treatment of cardiovascular disease. Combining aspirin and ticagrelor increases the risk of bleeding over that of either treatment when given alone, but it is standard clinical practice (and within ticagrelor's licence) to do so, and we will limit participant's exposure to a single loading dose of ticagrelor. Interactions with other drugs will not be an issue as those receiving any regular medication at screening will be excluded from participation.

Known side effect profiles

Aspirin (Aspirin lysine)

Reported side effects of aspirin (Aspirin lysine), taken from the current SmPC, include:

More common:

- Increased bleeding tendency (e.g. nose bleed, bleeding gums, bruises, intestinal bleeds and bleeding due to trauma). It is normal to note increased bleeding with cuts or spontaneous bruising with any dose of aspirin.
- Stomach irritation. This is usually mild and, if necessary, can often be treated with acid-lowering medications. There is some evidence that lower doses of aspirin have a lower chance of causing irritation than high doses.

Less common side effects of aspirin:

- Rhinitis, shortness of breath and itching have been reported uncommonly (up to 1 in 100 patients).
- Blood count abnormalities, allergic reactions, bleeding into the brain, inflammation of the blood vessels, asthma, heavy periods, nausea and vomiting have been reported rarely (up to 1 in 1000).
- Other cases of renal failure, water retention, stomach or intestinal ulceration, headache, ringing in the ears, reduced hearing, vertigo and diarrhoea have been reported (exact chance not known).

Ticagrelor

Reported side effects of ticagrelor include the following (reproduced from the current SmPC [37]):

Category	Very common	Common	Uncommon
Neoplasms benign, malignant and unspecified (including cysts and polyps)			Tumour bleeding ^a
Blood and lymphatic system disorders	Blood disorder bleeding ^b		
Immune system disorders			Hypersensitivity including angioedema ^c
Metabolism and nutrition disorders	Hyperuricaemia ^d	Gout/Gouty Arthritis	
Psychiatric disorders			Confusion
Nervous system disorders		Dizziness, syncope, headache	Intracranial haemorrhage
Eye disorders			Eye haemorrhage ^e
Ear and labyrinth disorders		Vertigo	Ear haemorrhage
Vascular disorders		Hypotension	

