Period 1: Day 1 - Day 10 (to 14)

- Participants will receive one of the following antiplatelet medication regimens for 10 to 14 days:
 - No IMP
 - No aspirin but a loading dose of ticagrelor (180 mg) taken on the last day of the medication period, 1 hour prior to endotoxin injection
 - Aspirin (aspirin lysine) 20 mg BD (only)
 - Aspirin (aspirin lysine) 20 mg BD, and a loading dose of ticagrelor (180 mg) taken on the last day of the medication period, 1 hour prior to endotoxin injection
 - Aspirin (aspirin lysine) 75 mg OD (only)

- Aspirin (aspirin lysine) 75 mg OD, and a loading dose of ticagrelor (180 mg) taken on the last day of the medication period, 1 hour prior to endotoxin injection
- Aspirin (aspirin lysine) 300 mg OD (only)
- Aspirin (aspirin lysine) 300 mg OD, and a loading dose of ticagrelor (180 mg) taken on the last day of the medication period, 1 hour prior to endotoxin injection

Visit 3 - Period 1: Day 11 (to 15)

On arrival

- Vital signs
- Physical examination
- Adverse event recording
- Concomitant medication recorded
- IMP compliance check for period 1
- Medically-qualified member of the research team to confirm that the withdrawal criteria (section 7.10) are not met, prior to proceeding further with visit

-1 hour (1 hour before endotoxin injection)

- IV cannula insertion (x2, one in each arm)
- 35.5 ml venous blood sample for baseline lab safety (full blood count, urea & electrolytes [sodium, potassium, urea and creatinine], liver function tests, clotting screen), cytokines, prostanoids, inflammatory markers and platelet function
- Bleeding time measurement
- Urine sample for prostanoid assessment at baseline
- Receive last dose of aspirin of period 1, or last dose of aspirin plus a loading dose of ticagrelor (180 mg), or no IMP, as directed by randomisation allocation
- Collect unused study medication and perform drug accountability check (sachet/pill count)
- Infusion of 250 ml 0.9% saline over 30 minutes
- 23 ml venous blood at 60 minutes after last dose of oral antiplatelet medication or equivalent time if not receiving IMP during period 1 (just before endotoxin administration)

0 hour (time of endotoxin injection)

- Continuous cardiac monitoring starts
- *E.coli* endotoxin 2 ng/kg intravenously administered over 1 minute
- Vital signs at 5, 15 and 30 minutes post-endotoxin
- Continuous IV infusion of 250 ml 0.9% saline over 1 hour
- 14 ml venous blood sample at 30 minutes post endotoxin

1 hour post endotoxin injection

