7.10 Withdrawal or postponement criteria

Subjects may be withdrawn or may discontinue from the trial if the following occur:

- Inability to insert intravenous cannula and/or obtain venous blood samples
- Withdrawal of consent
- Development of an intolerable adverse event due to study participation as determined by the investigator and/or subject
- Development of an intercurrent illness, condition or procedural complication that would interfere with the subject's continued participation, unless further study activities can be appropriately postponed (see section 7.10.1)
- At the time of planned endotoxin injection, receipt of a non-study medication in the preceding 48 hours that, in the opinion of the investigator, is likely to affect inflammation, thrombosis or haemostasis, unless the endotoxin injection visit can be appropriately postponed (see section 7.10.1)
- Poor compliance (<80% of doses taken) with study aspirin (aspirin lysine) during the preceding medication period, unless the endotoxin visit can be appropriately postponed (see section 7.10.1) to achieve 80 % compliance
- Violation of the protocol
- The investigator feels it is medically in the best interest of the subject to discontinue the subject's participation in the study
- Previously unknown data becoming available raising concern about the safety of the study drugs, so that continuation could cause potential risks to the subjects

The reason for withdrawal/discontinuation will be documented in the Case Report Form (CRF).

Withdrawn participants who receive at least one dose of IMP or endotoxin will be followed up by telephone at 10-14 days after withdrawal, and additionally all who discontinue due to adverse events (AEs) will be followed up until resolution or stabilisation. All outcomes of AEs will be recorded in the CRF.

Withdrawn participants who have proceeded to randomisation will not be replaced.

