8.7 Dosage modifications

Discontinuation of aspirin (aspirin lysine) and/or withholding ticagrelor may be considered in the following circumstances:

Major bleeding, including life-threatening bleeding

Intolerable adverse reaction such as minor bleeding that cannot be controlled by local measures

Discovery of severe thrombocytopenia (platelet count < 50,000/µL)

No dose adjustment beyond that specified by the randomisation schedule will be permitted.

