9.2 Operational definitions for (S)AEs

Adverse events and reactions will be recorded and reported from randomisation to 10 days after visit 3 (first endotoxin injection day), and from visit 6 (start of period 2) to 10 days after visit 7 (second endotoxin injection day). Thus, adverse events occurring in the break between the first and second medication periods, excepting those originating in the 10 days after endotoxin injection, will not be recorded or reported.

All SAEs will be reported to the sponsor within 24 hours of the research team becoming aware of them. This will be using the sponsor's proforma which will be sent by email to a dedicated address provided

specifically for this purpose. A copy will be kept in the trial master file and the AE log will be completed. All SAEs will be reviewed at the regular trial management group meetings.

All other AEs not meeting the criteria for reporting as serious will be recorded in the CRF, with the exception of the following events which will not be reported, as they can be expected as a normal response to endotoxin:

- Abnormal body temperature, excepting if $>39^{\circ}\text{C}$ and $<34^{\circ}\text{C}$, unless this persists at 6 hours post-endotoxin or meets the criteria for reporting as an SAE.
- Change in pulse rate, excepting pulse rates of >140 bpm and <45 bpm or if meeting the criteria for SAE reporting.
- Change (increase or decrease) in systolic or diastolic blood pressure from baseline of <40 mmHg unless meeting the criteria for SAE reporting.
- Self-limiting symptoms wholly due to endotoxaemia, for example fever, rigors, general malaise, nausea, vomiting or headache, at the discretion of the investigator, unless meeting the criteria for SAE reporting.
- Alterations in leukocyte (or subset) counts, platelet count or C-reactive protein unless meeting the criteria for SAE reporting.

The investigators will assess the relatedness of adverse events to the IMPs (aspirin [aspirin lysine], ticagrelor) and NIMP (endotoxin).

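### The adverse-event exemption for platelet, leukocyte and CRP changes is not confined to samples taken after endotoxin, so non-serious platelet falls on aspirin can go unreported

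*Protocol*

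**What the plan says.** Protocol 9.2 opens AE recording at randomisation and sends non-serious events to the CRF, "with the exception of the following events which will not be reported, as they can be expected as a normal response to endotoxin". The last item on that list is "Alterations in leukocyte (or subset) counts, platelet count or C-reactive protein unless meeting the criteria for SAE reporting". After the list, investigators are asked to judge relatedness to aspirin, ticagrelor and endotoxin.

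Protocol 7.7 places the on-treatment safety bloods under the -1 hour heading of visits 3 and 7: "35.5 ml venous blood sample for baseline lab safety (full blood count" and the other safety tests. Appendix 1 labels that row as taken before the drug dose.

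Three other sections bear on the point:
- Section 2.1 lists among the rarer aspirin side effects "Blood count abnormalities, allergic reactions, bleeding into the brain" and others.
- Section 8.7 gives "Discovery of severe thrombocytopenia" as one circumstance in which stopping aspirin or withholding ticagrelor can be considered.
- Section 7.10 says that "all who discontinue due to adverse events (AEs) will be followed up until resolution or stabilisation", and that the reason for any discontinuation goes in the CRF.

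Section 10.3.1 of both the protocol and the SAP reports the full blood count from visit 1 only.

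**The concern.** The exemption rests on a reason, endotoxin, that has not yet acted when the on-treatment platelet counts are drawn. At visit 3 the participant has had 10 to 14 days of the allocated regimen and no endotoxin. An abnormal count there reflects study aspirin, another illness or chance.

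Read literally, a non-serious fall in platelets found on a sample drawn for safety would not be reported as an AE. It would then have no assured route to the relatedness assessment in 9.2 or to the follow-up of adverse reactions in 9.9, and it would appear in no planned table. The trial has no formal data monitoring committee (protocol section vi) and relies on the protocol's own safety procedures, so gaps in those procedures matter more than they otherwise would.

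**Working it through.** **1. How many full blood counts are scheduled, and when.** Appendix 1 gives 4 ml per safety full blood count and a column total of 16 ml. Four draws (visit 1, visit 3 pre-dose, visit 6, visit 7 pre-dose) give 4 × 4 = 16 ml, which reproduces it.

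The grand total is a second check. One endotoxin day is 35.5 + 23 + 14 + 14 + 14 + 23 + 23 + 14 + 14 = 174.5 ml. All visits are 12.5 + 27 + 2 × 174.5 + 12.5 = 401 ml, as stated. One further full blood count after endotoxin on each day would have given 16 + 8 = 24 ml and 401 + 8 = 409 ml.

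The post-endotoxin rows are filled by the other tubes: 4.5 + 5 + 4.5 = 14; 9 + 5 + 9 = 23 at 2 hours; 4.5 + 5 + 9 + 4.5 = 23 at 3 hours.

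Two caveats on the table, neither of which changes the count:
- The visit 2 row is garbled in the text copy. Its 27 ml equals 4 + 4.5 + 5 + 9 + 4.5 (storage, cytokine plasma, serum, aggregometry, white cells), with no room for a full blood count, and visit 2 is before treatment.
- The plasma column adds to 4.5 + 2 × (8 × 4.5 + 9) = 94.5 ml against a stated 99. This does not touch the full blood count column.

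**2. Drug and endotoxin status at each count.**

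| Count | Study aspirin | Endotoxin |
|---|---|---|
| Visit 1 | not started | none |
| Visit 3, -1 h | 10–14 days | none yet |
| Visit 6 | off; period 2 starts next morning | near the end of the 5 to 18 week washout |
| Visit 7, -1 h | 10–14 days | at least 35 + 10 = 45 days earlier |

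Section 2.1 says the endotoxin response subsides by 6 hours. So 2 of 2 on-treatment counts precede that day's endotoxin, and no scheduled platelet count can show an acute endotoxin effect. Both are also before the ticagrelor dose, so any drug effect they show would be aspirin's.

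**3. Leukocytes and CRP differ.** Section 7.7 schedules the white cell count and differential before and repeatedly after endotoxin, and CRP before and at 6 hours after. For the later samples the stated reason is apt. Both are analysed by aspirin regimen in 10.3.3. No platelet count is named among the post-endotoxin tests or in any planned analysis.

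**4. The other items on the list carry limits.** Temperature has numeric bounds and a time condition, "unless this persists at 6 hours post-endotoxin or meets the criteria for reporting as an SAE". Pulse and blood pressure have numeric bounds. The symptom item is confined to "Self-limiting symptoms wholly due to endotoxaemia". The laboratory item has only the SAE exception.

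**5. Size.** Six of the eight sequences contain aspirin: 72 × 6/8 = 54 participants, and 54 × 2 = 108 on-aspirin counts if all complete. With 16 completers per group (10.1), completers contribute 16 × 3 × 2 = 96. At the interim, the 83 endotoxin visits expected in 10.6, split evenly over eight regimens, give 83 × 6/8 ≈ 62. Section 2.1 puts aspirin blood count abnormalities at up to 1 in 1000; applied to 54 participants, that is at most 54 × 0.001 ≈ 0.05 expected cases.

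**The case against.** The strongest reply is that the list is introduced as normal endotoxin responses and followed by a relatedness assessment. An investigator reading for purpose would not exempt a result obtained before any endotoxin. That is a sensible reading, but the introduction gives a reason and does not make it a condition, and four of the five items needed their own limits.

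Four stronger inferences are tempting, and the documents do not support them.
- *That all such changes are exempt.* Changes meeting SAE criteria stay reportable, and 9.1 allows an important medical event to be classed as serious. That route is a matter of judgement with no platelet criterion, so lesser falls remain exempt.
- *That 9.2 and 8.7 contradict each other outright.* Section 9.2 governs reporting and leaves the AE definition in 9.1 unchanged; 8.7 is permissive and sets no reporting rule. Both can be followed. What is unclear is how a finding acted on under 8.7 is recorded, and whether the 7.10 follow-up for discontinuation due to an AE then applies.
- *That every post-randomisation count is affected.* Counting visits 3, 6 and 7 in all 72 participants would mix in off-drug visit 6 samples, where eligibility is rechecked, and controls who take no aspirin.
- *That infection before the challenge would be missed.* Intercurrent illness is not on the list, and visits 3 and 7 require examination, AE recording and a check of the withdrawal criteria before proceeding.

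It is also fair that 10.3.1 is a baseline summary, so its restriction to visit 1 is no omission in itself. The on-treatment platelet counts still have no planned table elsewhere.

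**Conclusion.** The point holds for platelets. As worded, the exemption covers up to 108 scheduled on-aspirin counts to which its stated reason cannot apply, and a non-serious fall could pass without an AE report or a table. For leukocytes and CRP it holds only for AE recording of abnormal pre-endotoxin values.

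Loss of a severe thrombocytopenia is possible, not certain: it may be classed as serious, and if it led to discontinuation the reason would be in the CRF. The number of affected events is probably very small.

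This rests on a literal reading of 9.2, on Appendix 1 listing all scheduled platelet counts, and, for the 108, on the planned 54 aspirin participants completing both periods. Allocation is by simple randomisation, so the realised number may differ. The change is worth making because it closes a gap in safety capture at almost no cost.

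**What to change.** - In 9.2, limit the laboratory item to samples taken after that day's endotoxin injection, and say when the window closes. Abnormal values on the visit 6 sample and on the pre-endotoxin samples at visits 3 and 7 then follow the ordinary AE rules.
- Reconcile 9.2 with 8.7 and 7.10: state how a laboratory finding that leads to discontinuation is recorded and which follow-up applies. No clinical threshold or stopping rule is proposed here.
- In SAP 10.3, add a table of the visit 3 and visit 7 pre-dose platelet counts by aspirin regimen, with visit 1 for reference.

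The cost is some rewording, one extra table from blood already drawn, and possibly a few more non-serious AE entries. No additional sampling is needed.

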9.3 Recording and reporting of SAEs, SARs AND SUSARs

SAEs/SUSARs will be recorded and reported from randomisation to 10 days after visit 3 (first endotoxin injection day), and from visit 6 (start of period 2) to 10 days after visit 7 (second endotoxin injection day). Thus, adverse events occurring in the break between the first and second medication periods, excepting those originating in the 10 days after endotoxin injection, will not be recorded or reported.

These must be recorded on the Sheffield Teaching Hospitals NHS Foundation Trust SAE reporting Form and emailed to the Sponsor's dedicated email address for this purpose **within 24 hours** of the research staff becoming aware of the event.

For each **SAE or SUSAR** the following information will be collected:

- full details in medical terms and case description
- event duration (start and end dates, if applicable)
- action taken
- outcome
- seriousness criteria
- causality (i.e. relatedness to trial drug / investigation), in the opinion of the investigator
- whether the event would be considered anticipated.

Any change of condition or other follow-up information should be emailed to the Sponsor as soon as it is available or at least within 24 hours of the information becoming available. Events will be followed up until the event has resolved or a final outcome has been reached.

All SAEs assigned by the PI or delegate as both suspected to be related to IMP-treatment and unexpected will be classified as SUSARs and will be subject to expedited reporting to the Medicines

and Healthcare Products Regulatory Agency (MHRA). The sponsor will inform the MHRA, the REC and the relevant Marketing Authorisation Holder(s) of SUSARs within the required expedited reporting timescales.

SAEs related to the NIMP (endotoxin) will be reported by the investigators to the sponsor, but further forwarding to other agencies will not be required, as per European Directive 2011/C 172/01. NIMP-related SAEs will be evaluated by the sponsor and investigator team with regard to ongoing safety implications. If there are ongoing safety implications for the trial then these will be addressed via urgent safety measure, substantial amendment or termination of the trial.

If, on adjudication by the investigators, there is a possibility that an SAE is related to interaction between the NIMP and at least one of the IMPs, the process will be followed for reporting this as an IMP-related event, including any required onward notification by the sponsor concerning the relevant IMP.

If an SAE is judged as possibly related to both NIMP and an IMP then it will be assessed with regard to expectedness with regard to the IMP and reported onwards as a SUSAR if it is judged to be unexpected in relation to the IMP

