- Vital signs at 1 hour and 1.5 hours post endotoxin injection
- Continuous IV infusion of 250 ml 0.9% saline over 1 hour
- 14 ml venous blood sample at 1 hour post endotoxin
- Urine sample at 1 hour post endotoxin
- 14 ml venous blood sample at 1½ hours post endotoxin

2 hours post-endotoxin injection

- Vital signs at 2 hours post endotoxin
- Continuous IV infusion of 250 ml 0.9% saline over 1 hour
- 23 ml venous blood sample at 2 hours post endotoxin
- Urine sample at 2 hours post endotoxin

3 hours post-endotoxin injection

- Vital signs at 3 hours post endotoxin
- 23 ml venous blood sample at 3 hours post endotoxin
- Bleeding time measurement at 3 hours post endotoxin

4 hours post-endotoxin injection

- Vital signs at 4 hours post endotoxin
- 14 ml venous blood sample at 4 hours post endotoxin
- Urine sample at 4 hours post endotoxin

6 hours post-endotoxin injection

- Vital signs at 6 hours post endotoxin
- 14 ml venous blood sample at 6 hours post endotoxin
- Urine sample at 6 hours post endotoxin
- Continuous cardiac monitoring ends

Visit 4 (Period 1, 1 day after visit 3)

- Telephone follow-up for adverse events
- Facility to convert to in-person visit if any concerns raised

There will then follow a washout period of at least 5 weeks, and not more than 18 weeks, between the first endotoxin challenge day and the beginning of the second medication period. This is to avoid reliably any tolerance of the response to endotoxin, a phenomenon absent by 5 weeks [39].

Visit 5 (10 to 14 days after visit 3)

- Telephone follow-up for adverse events

Visit 6 (Period 2, Day 0)

- Vital signs (BP, pulse, temperature)
- Physical examination
- Adverse event recording
- Concomitant medication recording
- Medically qualified investigator to confirm eligibility criteria again (see section 6) and that no withdrawal criteria (section 7.10) are met at this point prior to proceeding to medication period 2
- Laboratory safety blood tests: 12.5 ml venous blood for full blood count, urea & electrolytes (sodium, potassium, urea and creatinine), liver function tests, clotting screen
- Medication dispensed for period 2
- Dosing training for use of aspirin lysine if required

Participants will be advised to begin antiplatelet medication, allocated as follows, for period 2 from the morning after visit 6:

- If received no IMP in period 1, to receive no aspirin, but a loading dose of ticagrelor (180 mg) 1 hour before endotoxin injection in period 2.

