7.8 Long term follow-up assessments

Participants will be followed up 10 (to 14) days after the second endotoxin injection day (Period 2, Day 21) by telephone. Any new adverse events will be recorded. Participants will be thanked for their involvement in the study and arrangements made to provide the monetary reimbursement due to them. In the event of a participant remaining uncontactable at the end of the follow up window, we will interrogate the hospital records of the participant to clarify vital status and any evidence of untoward events. Participants will be declared 'lost to follow up' if they are uncontactable 28 days after the second endotoxin injection day. A file note will be made in this instance.

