9.5 Notification of deaths

- o Any deaths will be treated as an SAE and reported accordingly to the sponsor using the SAE reporting procedures within 24 hours of becoming aware, irrespective of whether the death is related to the IMP, endotoxin administration or an unrelated event.

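### Sections 9.2 and 9.3 suspend adverse event reporting, including SAEs and SUSARs, for about 24–25 to 115–116 days between challenges, in conflict with other reporting duties in the protocol

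*Protocol*

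**What the plan says.** Section 9.2 sets the window for all events: "Adverse events and reactions will be recorded and reported from randomisation to 10 days after visit 3 (first endotoxin injection day"), and then from visit 6 to 10 days after visit 7. Section 9.3 repeats it for serious events: "SAEs/SUSARs will be recorded and reported from randomisation to 10 days after visit 3 (first endotoxin injection day), and from visit 6" to 10 days after visit 7. Both sections spell out the consequence: "Thus, adverse events occurring in the break between the first and second medication periods, excepting those originating in the 10 days after endotoxin injection", are to be neither recorded nor reported. Section 9.9 is in line with this, since it asks for indefinite follow-up only of SUSARs that begin inside the reporting period.

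Section 7.7 sets the washout at 5 to 18 weeks, measured "between the first endotoxin challenge day and the beginning of the second medication period". Period 2 dosing starts the morning after visit 6.

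Other parts of the protocol carry no such window:

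- Section 9.2, second paragraph: all SAEs go to the sponsor within 24 hours of awareness, and all are reviewed by the trial management group (TMG).
- Section 9.4, item 4 for the principal investigator: responsible for recording and reporting all SAEs.
- Section 9.5: "Any deaths will be treated as an SAE and reported accordingly to the sponsor using the SAE reporting procedures within 24 hours" of awareness.
- Section 7.7: a safety call headed "Visit 5 (10 to 14 days after visit 3"), and an adverse event recording item at visit 6.
- Section 7.8, on the call 10 to 14 days after the second challenge: "Any new adverse events will be recorded".

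The SAP does not settle the matter. Its section 10.7 says who is in the safety set, not which calendar period counts.

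**The concern.** Every participant who continues receives a second endotoxin dose after the break. Those on aspirin repeat the same regimen, and those who had no ticagrelor in period 1 receive it in period 2. Section 2.1 acknowledges that the combination carries more bleeding risk than either drug alone.

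The trial has no data monitoring committee. Section vi relies instead on the protocol's safety procedures, including discussion of any SAE with the sponsor. Section 9.3 adds sponsor evaluation of endotoxin-related SAEs for continuing safety implications. None of these works on an event that is never recorded.

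A site that follows 9.3 literally would keep a serious event in the break from the sponsor, the TMG and the safety tables. A site that follows 9.4 would report it.

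**Working it through.** The documents state no gap length, so there is no figure to reproduce. The check is calendar arithmetic and then a comparison of sections.

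**Length of the gap.** Inputs: washout of 5 to 18 weeks from the first challenge to the start of period 2 dosing (sections 4 and 7.7); recording closes 10 days after visit 3 and reopens at visit 6 (9.2, 9.3). Gap = 7 × weeks − 10.

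- Shortest: 7 × 5 = 35 days; 35 − 10 = 25 days.
- Longest: 7 × 18 = 126 days; 126 − 10 = 116 days.

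If visit 6 is the day before dosing starts, each figure falls by one, to 24 and 115 days. The uncovered share of the washout is 25/35 = 71% to 116/126 = 92%. This is a share of calendar time, mostly off drug, and does not measure exposure.

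The last scheduled contact before visit 6 is the visit 5 call. If it is made on day 14, 35 − 14 = 21 to 126 − 14 = 112 days remain until the washout ends. The second challenge is on day 11 to 15 of period 2, which is 10 to 14 days after dosing starts: days 45 to 49 after the first challenge on the shortest washout, days 136 to 140 on the longest.

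**What a site should do with a given event.**

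| Event | Exclude | Include |
|---|---|---|
| SAE on day 12, disclosed in a day 14 visit 5 call | 9.2 first paragraph, 9.3 | 9.2 second paragraph, 9.4; visit 5 call for adverse events (7.7) |
| SAE in the break, disclosed at visit 6 | 9.2 first paragraph, 9.3 | 9.2 second paragraph, 9.4; visit 6 AE item (7.7), if it looks back |
| Death in the break | 9.3 (general rule) | 9.5 (specific rule) |
| New AE on days 11 to 14 after visit 7 | 9.2, 9.3 | 7.8 |

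The protocol does not say whether the visit 6 item looks back over the break. Nearly all the time since visit 5 lies in the excluded period, so the item is either almost empty or in conflict with 9.2.

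**A related anchoring conflict.** Section 7.7 places visit 8 one day, and visit 9 10 to 14 days, after visit 6. Visit 6 is Day 0 and visit 7 is Day 11 to 15. Visit 9 as written therefore falls between 10 − 15 = −5 and 14 − 11 = +3 days from the second challenge. Section 7.8 instead counts 10 to 14 days from the second challenge. This matters for the fix, because a reporting window tied to visit 9 as written could close around that challenge.

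**The case against.** The strongest defence is that the exclusion is deliberate. It appears in the same terms in 9.2 and 9.3 and covers a largely off-treatment interval. Ticagrelor is a single dose, endotoxin symptoms typically settle by 6 hours (section 2.1), and collection runs 10 days past the challenge. Sequence 1 receives no IMP in period 1, so no IMP-related reaction can arise in its break. This makes a light rule for non-serious events reasonable. It does not justify leaving SAEs out. Causality is left to the investigator's judgement of each event, the documents give no reason for a 10-day limit on serious events, and the unwindowed duties remain.

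Three stronger readings are tempting, but the documents do not support them.

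- *Participants are re-exposed blind.* Visit 6 requires adverse event and concomitant medication recording, physical examination, safety bloods, and a medically qualified re-check of eligibility and withdrawal criteria before period 2. Section 7.10 requires the reason for any withdrawal to be documented. A serious event may well come to light clinically.
- *Deaths in the break go unreported.* Section 9.5 deals specifically with any death, related or not, without a window, and the specific rule is the natural one to follow.
- *Reporting a serious event in the break is forbidden.* That treats one side of a contradiction as settled. The 9.2 and 9.4 duties cover all SAEs.

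One could reply that the general duties are meant to be read within the stated window. If so, much of the contradiction goes, but the gap in SAE reporting becomes definite.

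**Conclusion.** The point holds as a gap and a contradiction in sponsor safety reporting. On the wording of 9.2 and 9.3, serious events are outside reporting for about 24–25 to 115–116 days before the second challenge, for everyone who goes on to period 2. Other sections require the same events to be reported. Days 11 to 14 after each challenge are in the same conflict.

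The figures assume that the washout limits are kept and that visit 6 falls on, or the day before, the end of the washout. The documents give no expected number of serious events in the break, and in healthy volunteers few would be expected, so the size is in days uncovered and not in events missed. The primary efficacy result is not affected. The change should be made because sponsor review stands in for a monitoring committee and the correction is cheap.

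**What to change.** 1. In 9.2 and 9.3, record and report SAEs, SARs, SUSARs and deaths continuously from randomisation to the final telephone follow-up. Limit the break exemption to non-serious AEs, and align 9.9 with the new period.
2. Extend the AE window after each challenge to the date of the 10 to 14 day call, anchored to visit 3 and to visit 7, so that it matches 7.7 and 7.8.
3. Reconcile the timing of visits 8 and 9 in 7.7 (counted from visit 6) with 7.8 (counted from the second endotoxin day). Do not define the second window by visit 9 until this is done.
4. State that adverse event recording at visit 6 asks about serious events since visit 5.

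No new visits are needed, since the calls and visit 6 are already scheduled. The cost is a protocol amendment, with sponsor assessment and whatever approvals follow under 13.10, and a few extra reports, most of them unrelated to treatment.
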